7.1. Adverse events

Adverse events are recorded in the electronic case report form (eCRF) created for each patient (see Chapter 9) and, if clinically relevant, communicated to the patient and appropriate measures initiated. If desired, the patient's family doctor can also be informed. Any necessary follow-up checks or further measures are primarily carried out by the attending physician in the rheumatology outpatient clinic or are initiated by them.

7.2. Safety

A request was submitted to HDI-Gerling to register patient insurance as soon as a final positive vote from the ethics committee is available.

8. Evaluation of data

8.1. Case number estimate

The case number estimate was carried out in collaboration with [name] and resulted in a total number of 12 participants. The complete case number estimate is attached to the study protocol.

8.2. Biometric analyses and data evaluation

Due to the number of cases, the statistical evaluation mainly comprises exploratory analysis methods. The primary question (maximum tracer uptake in the ILD area versus normal lung tissue) is evaluated using Kendall's tau correlation coefficient.

If possible, subgroups could be examined in relation to limited vs. extensive ILD (Goh et al. 2008) with regard to stratification analogous to the INBUILD study (Flaherty et al. 2019) and with regard to the EUSTAR activity index (Valentini et al. 2017).

9. Data protection, data storage

Personalized data will be collected as part of the study. External cooperation partners, such as the statistician conducting the analysis, will only receive personal data in pseudonymized form. The data will be anonymized for the purpose of scientific publication in a peer-reviewed journal.

The data will be stored in locked rooms at the rheumatology outpatient clinic (A3, -1, ZIM) and on the UKW servers. At the end of the evaluation, but no later than after 10 years, the data collected as part of the study will be anonymized and personal data will be deleted. Any remaining sample material will be destroyed.

Until the data is anonymized, patient-related data records can be deleted and any samples that may be available can be destroyed if the patient revokes their consent.

All data is subject to the data protection regulations applicable throughout the clinic. Test subject data will not be passed on to third parties. The names of the test subjects and all other confidential information are subject to confidentiality and the provisions of the Federal Data Protection Act (BDSG). The pilot study is for research purposes only and its data will not be used (even in the future) for a consultation evaluation procedure.

All patient-related data is recorded in pseudonymized form, and an Excel-based eCRF is created for each patient. Each patient is uniquely identified by a patient number assigned during registration. [name] maintains a confidential patient list in which the pseudonyms are linked to the full patient names. The evaluation of the collected image data is stored in SAP as a findings document. The data collected for the evaluation of the pilot series is also stored as a pseudonymized Excel file, which contains only the data and the study code of the respective patient.

The blood samples of the participating patients are generally used directly for analysis and then destroyed. In the event that a new analysis is necessary, which only occurs during the course of the study, part of the blood is frozen and stored in pseudonymized form in our in-house immunological laboratory in the rheumatology department. After completion of the study, but no later than ten years, the blood samples will be destroyed. Only physicians and medical-technical assistants involved in the study have access to the blood samples.

The data protection provisions in accordance with the EU General Data Protection Regulation (GDPR) are complied with. The legal basis for data processing is the consent of the study participants (Art. 6 (1a) and Art. 9 (2a) of the GDPR). Participants may request information about the stored data from the UKW within the framework of the legal requirements; if incorrect personal data is processed, participants have the right to have it corrected. They may request the deletion of personal data or the restriction of processing or data transfer. If these rights are asserted against the UKW, it will be examined whether these rights are subject to any restrictions.

10. Consent

Participation in this study is voluntary; consent can be withdrawn at any time without giving reasons (see also "Data protection"). There is no connection between the treatment of patients and participation in the study.

11. Ethics

The project complies with the Declaration of Helsinki (as of October 2013, Fortaleza, Brazil) and Good Clinical Practice.

The protocol and patient information with consent form will be submitted to the local, independent ethics committee of the Medical Faculty of the University of Würzburg.

12. Publication of data

The results or parts of the results of the study are to be published in peer-reviewed scientific journals in anonymized form.

13. Literatur

Bundesamt für Strahlenschutz, Natürliche Strahlung in Deutschland (letztmalig abgerufen am 9.2.2022): https://www.bfs.de/DE/themen/ion/umwelt/natuerliche-strahlung/natuerliche-strahlung_node.html

Cipriani P et al. Differential expression of stromal cell-derived factor 1 and its receptor CXCR4 in the skin and endothelial cells of systemic sclerosis patients: Pathogenetic implications. *Arthritis Rheum.* 2006 Sep;54(9):3022-33. doi: 10.1002/art.22047.

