| STUDY DESIGN | Explorative, prospective pilotstudy, not blinded, not randomized |
| PRIMARY ENDPOINT | Measurement of the maximum measurable 68Ga-pentixafor tracer activity in CXCR4-PET/CT |
| DURATION | Ca. 1 year |
| NUMBER OF CENTERS | Monocentric at the University Hospital Würzburg |

3. Background

Interstitial lung disease (ILD) is the most common cause of death in patients with systemic sclerosis (SSc). With regard to the pathogenesis of ILD, but also of other manifestations of SSc, it is postulated that leukocytes initially migrate into the tissue and cause an inflammatory reaction, which subsequently leads to fibrosis. Active inflammation can be treated much more effectively with medication than fibrosis.

The distinction between fibrosis that has already occurred, i.e., is usually irreversible, and the active stage with inflammation is therefore of great therapeutic importance.

Stromal cell-derived factor 1 (SDF-1 or synonymously CXCL12) and its receptor C-X-C motif chemokine receptor 4 (CXCR4) are involved in angiogenesis and the mediation of leukocyte migration, which is an important pathomechanism in SSc. Consistent with this, high SDF-1 and CXCR4 expression is found in the skin of SSc patients, especially in the early stages of the disease, which decreases with increasing disease duration (Cipriani et al. 2006).

SSc patients may have antibodies against CXCR4. Higher antibody titers are associated with more severe lung involvement and poorer lung function. CXCR4-positive mononuclear cells from peripheral blood are found to be reduced in SSc (Weigold et al. 2018).

The consideration of the CXCR4/CXCL12 axis in SSc therefore appears promising.

The Clinic and Polyclinic for Nuclear Medicine at Würzburg University Hospital has a manufacturing license (issued by the Regional Council of Upper Franconia) for the production of 68Ga-Pentixafor for imaging the chemokine receptor CXCR4. CXCR4 is expressed by many cells of the hematopoietic system, such as stem cells, neutrophil granulocytes, monocytes, T lymphocytes, B lymphocytes, pre-B cells, dendritic cells, and macrophages. It is also detectable on most malignant cells.

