During inflammatory processes, CXCL12, the ligand of CXCR4, is upregulated in the affected tissue. The chemotactic effect of this ligand leads to the migration of CXCR4-positive cells into the inflamed area, which can be visualized in PET using the CXCR4-specific tracer 68Ga-Pentixafor. A significant advantage over the previous standard tracer F-18 deoxyglucose is its independence from glucose metabolism.

Based on experience gained in the use of CXCR4-PET/CT in malignant diseases in studies conducted at the University Hospital of Würzburg, it can be assumed that this new tracer should enable sensitive visualization of inflammatory processes in SSc and thus functional imaging. This assumption is supported by the fact that CXCR4 can be visualized using PET/CT in idiopathic pulmonary fibrosis (IPF) – a clinical picture that is very similar to ILD in SSc in terms of clinical presentation, prognosis, and treatment (Derlin et al. 2021).

To date, only non-functional cross-sectional imaging using chest CT, which is routinely performed every 1-2 years, has been established for the diagnosis and monitoring of pulmonary fibrosis in SSc.

4. Aims of the study

Testing the hypothesis that tracer activity in ⁶⁸Ga-pentixafor PET/CT correlates with disease activity in the lungs (heart, and skin) and that activity is associated with disease progression, i.e., worsening fibrosis in the corresponding organ.

Another objective of the study is to characterize CXCR4 expression in monocytes, granulocytes, and lymphocytes in peripheral blood using flow cytometry and, if necessary, cell culture analysis, as well as to measure CXCL12 and CXCR4 antibodies in peripheral blood. The leukocyte populations mentioned above are particularly important for the pathogenesis of inflammatory changes in SSc. A correlation with ⁶⁸Ga-pentixafor uptake will be investigated.

A further objective is to correlate ⁶⁸Ga-pentixafor uptake with routinely available clinical, imaging, and laboratory parameters.

The aim is to use the data collected to perform a well-founded case number calculation for a subsequent prospective study.

5. Study design and endpoints

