5.2. Endpoints

The primary endpoint of the pilot series is to determine the maximum measurable ⁶⁸Ga-Pentixafor uptake in CXCR4-PET/CT in the area of fibrotic pulmonary changes.

Secondary endpoints:

- Determination of the maximum measurable ⁶⁸Ga-Pentixafor uptake in CXCR4-PET/CT in the heart
- Correlation of the measured tracer activity with clinical, laboratory, and imaging findings.

The secondary endpoints serve to classify the measured tracer activities should significant fluctuations occur within the group.

6. Course of the study

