All CT and PET examinations are initially evaluated visually to determine the intensity and extent of the inflammatory processes. For semi-quantitative assessment of regional inflammatory activity, regions of interest (ROI) are placed in areas of increased [^{68}Ga]-pentixafor uptake using TrueD software (Siemens Medical Solutions, Knoxville, TN). The SUV(mean/max/peak) is calculated within the ROI according to the formula:

SUV = specific activity concentration (Bq/g) x body weight (in g) / injected activity (Bq). In addition to the SUV, other standard quantification parameters, such as the CXCR4-positive volume or mathematically extracted items (e.g., radiomics parameters, Interview Fusion, Mediso Medical Imaging, Hungary), are determined. In [68Ga]-pentixafor PET/CT, the SUVs are correlated with tracer uptake in the background (e.g., in the liver) and a ratio is formed.

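### Section 8.2 words the primary question as ILD area versus normal lung but evaluates it with Kendall's tau on two unnamed variables; with regional values paired across patients, tau cannot show whether uptake differs between the regions

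*Protocol*

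**What the plan says.** Section 8.2 gives the primary question and its only method in one sentence: "The primary question (maximum tracer uptake in the ILD area versus normal lung tissue) is evaluated using Kendall's tau correlation coefficient". It calls the evaluation mainly exploratory.

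Other parts of the protocol bear on what was meant:

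- **Synopsis (section 2), primary endpoint:** "Measurement of the maximum measurable 68Ga-pentixafor tracer activity in CXCR4-PET/CT". It names no region and no comparator.
- **Section 5.2, primary endpoint:** the maximum "uptake in CXCR4-PET/CT in the area of fibrotic pulmonary changes". Normal lung is not mentioned.
- **Section 5.2, secondary endpoint:** "Correlation of the measured tracer activity with clinical, laboratory, and imaging findings".
- **Section 4:** the hypothesis is that tracer activity correlates with disease activity. A further aim is to use the data to "perform a well-founded case number calculation for a subsequent prospective study".
- **Section 6.4, image evaluation:** "regions of interest (ROI) are placed in areas of increased" tracer uptake, and SUVmean, SUVmax and SUVpeak are calculated there. Then "the SUVs are correlated with tracer uptake in the background (e.g., in the liver) and a ratio is formed". Normal lung is not named as a reference region.
- **Section 16, appendix:** the sample size is for a Pearson correlation of r = -0.75 between FVC and CXCR4 PET signal. The value comes from idiopathic pulmonary fibrosis because no comparable study in SSc-ILD was known.

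**The concern.** The question reads as a comparison of two lung regions, while the method measures association. Taken at face value, the two values per patient are maximum uptake in ILD and in normal lung, and tau is computed across patients. That coefficient says whether patients with high uptake in one region also tend to have high uptake in the other. It says nothing about which region takes up more tracer.

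The primary result would then not answer the question printed beside it. A significant tau could be taken as evidence that ILD uptake exceeds normal lung, and a small tau as evidence that it does not. Tau also gives no effect size or SD for the regional contrast, which the next study's sample size would need if that contrast is the question.

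**Working it through.** **1. The plan's own figure.** Inputs from the appendix: r = -0.75, two-sided alpha 0.05, power 0.80, Pearson correlation.

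- Fisher z: n = ((1.960 + 0.842)/atanh(0.75))² + 3 = (2.802/0.973)² + 3 = 11.29.
- Simulation under bivariate normality (400,000 runs per n): power 0.779 at n = 10 and 0.826 at n = 11.

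The stated 11 is reproduced, and the appendix raises it to 12 for 10% dropout. This N belongs to a correlation. No regional difference and no SD of such a difference enters it.

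**2. Why tau does not respond to a difference.** With x = normal-lung uptake and y = ILD uptake in n patients, and no ties:

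tau = S / [n(n-1)/2], where S = sum over pairs i < j of sign(x_i - x_j) × sign(y_i - y_j).

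Replace y by a + b·y with b > 0. Every sign(y_i - y_j) stays the same, so S, tau and its p-value stay the same. This needs no assumption about the data.

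**3. Worked example (invented values, n = 11).** Normal lung: 0.8, 0.9, ..., 1.8. ILD: k × (1.0, 0.8, 0.9, 1.2, 1.1, 1.4, 1.3, 1.6, 1.5, 1.8, 1.7). Of 55 patient pairs, 49 are concordant and 6 discordant, so S = 43 and tau = 43/55 = 0.782. At k = 1 the ILD values are the normal-lung values in another order, so the geometric mean ratio equals k.

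| k (ILD/normal) | tau | p (tau) | p (paired Wilcoxon, log ratios) |
|---|---|---|---|
| 1.0 | 0.782 | 0.0003 | 0.75 |
| 1.5 | 0.782 | 0.0003 | 0.001 |
| 3.0 | 0.782 | 0.0003 | 0.001 |

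The opposite case: for 12 invented patients with unrelated regional values about 3 SUV apart, tau is 0.18 (p = 0.46) and the paired Wilcoxon p is 0.0005.

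**4. Illustration by simulation.** All inputs are assumed and none is in the protocol: log-normal uptake, log SD 0.3, 0.5 or 0.7, ILD/normal ratio 1.0, 1.5 or 2.0, inter-region correlation 0, 0.5 or 0.8, n = 11, two-sided 0.05, exact critical values, 20,000 runs per cell.

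| Test | Setting | Rejection at correlation 0 / 0.5 / 0.8 |
|---|---|---|
| Tau | every SD, every ratio including 1.0 | about 4% / 26-27% / 78-79% |
| Wilcoxon | ratio 1.0, every SD | about 4% throughout |
| Wilcoxon | ratio 1.5, SD 0.3 | 77% / 97% / 100% |
| Wilcoxon | ratio 1.5, SD 0.5 | 36% / 63% / 95% |
| Wilcoxon | ratio 1.5, SD 0.7 | 20% / 37% / 74% |

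Tau's rejection rate follows the correlation and ignores the ratio. The paired test responds to the ratio, but its power at this size is not assured. A paired t-test has 80% power for a standardised paired difference of about 0.94 with 11 patients and 0.89 with 12.

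**5. Precision of a within-patient ratio.** The 95% CI runs from the estimate divided by a factor to the estimate times that factor, where factor = exp(t × SD × sqrt(2(1 - rho))/sqrt(n)). With n = 11, t = 2.228 and assumed log SD 0.5:

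- rho 0.8: exp(2.228 × 0.5 × 0.632/3.317) = 1.24
- rho 0: exp(2.228 × 0.5 × 1.414/3.317) = 1.61

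Over log SD 0.3 to 0.7 the factor runs from 1.14 to 1.94.

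**6. SUVmax and ROI size.** A maximum over more voxels tends to be larger. Assumed: identical voxel distributions in both regions, independent Gaussian voxels, within-ROI CV 0.1 to 0.3, log SD 0.15 per region, 11 patients. With ten times as many voxels in the ILD ROI, the ILD/normal ratio of SUVmax came out at about 1.06 to 1.12, and the Wilcoxon test rejected in about 9% to 30%. With equal ROIs the ratio was about 1.00, with 3% to 5% rejection.

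**The case against.** The strongest counter-argument is that an association was meant. A versus B is ordinary wording for a correlation, the sentence itself says correlation coefficient, section 4 states a correlation hypothesis, and the appendix sizes a correlation. For an association, tau suits a small sample. This stands as a possible reading. A reader might therefore infer from this point that the sponsor certainly intended a regional contrast and chose the wrong test; the documents do not establish that. But the association reading does not make the text right. Association between ILD and normal-lung uptake would be an odd primary question, and association with clinical, laboratory or imaging findings is secondary in 5.2. Either way 8.2 has to change.

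A second argument is that tau could be computed against a region label. That version would respond to a difference: in the second example in step 3 tau-b is 0.72, equivalent to a Mann-Whitney comparison. So tau is not blind under every coding. No such coding is described, however, and it would ignore the pairing within patient.

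A third is that a statistical analysis plan may name the variables. It may, but the protocol has already fixed a question and a method that do not fit each other on the natural reading, so this is more than detail left for later.

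Finally, the harm can be overstated. It is tempting to conclude that the primary endpoint is lost or that the aim of planning the next study is blocked. The documents do not support that: the endpoint in the Synopsis and 5.2 is a measurement that needs no test, and reporting tau does not prevent reporting SUVs with their means and SDs.

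**Conclusion.** The point holds in limited form and should be corrected. Section 8.2 pairs a question worded as a regional contrast with a coefficient that, for regional values paired across patients, is unaffected by the size of that contrast. This part is algebraic and rests only on the pairing. The rest of the protocol does not settle whether a contrast or an association was intended. The simulated rejection rates, CI factors and ROI-size figures rest on assumed inputs: the first only illustrate the invariance, and the other two only inform the remedy. The consequence is modest, because the pilot is exploratory, has no decision rule, and can report its uptake values regardless of tau.

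**What to change.** The sponsor should say which question was meant and align sections 8.2 and 5.2.

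**If a contrast was meant:**

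- In 5.2, name normal lung as the comparator.
- In 6.4, place the ILD and normal-lung ROIs by CT and make them equal in size. CT placement avoids selecting the ILD region for its high uptake, but alone it does not remove the bias of SUVmax towards the larger ROI. The alternative is to use SUVmean or SUVpeak, already calculated under 6.4; the endpoint would then no longer be worded as a maximum.
- In 8.2, report the within-patient ILD/normal ratio with a 95% CI and a Wilcoxon signed-rank test, or a paired t-test on logs.
- In 8.1, state that N = 12 was derived for a Pearson correlation and carries no stated power for this contrast. Give any expected precision as a range.

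The cost is the text edits and some extra ROI reading on the acquired images, with no extra scan or visit. Patients with little normal lung may be lost to the comparison: with 10 instead of 11 patients, at an assumed log SD of 0.5, the CI factor widens from 1.24-1.61 to 1.25-1.66.

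**If an association was meant:** name both variables in 8.2, delete the comparison with normal lung, and align 5.2, where correlation with clinical, laboratory and imaging findings is now secondary. This costs only a text edit.

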6.3. Recruitment and study procedure

Timeline of the pilot study:

- a. Screening of patients during their appointment at the rheumatology outpatient clinic
- b. Review of inclusion and exclusion criteria
- c. Inclusion in the pilot study
- d. Determination of baseline parameters:
 - i. mRSS
 - ii. Troponin/NT-pro-BNP
 - iii. Leukocyte differentiation (flow cytometry/cell culture), CXCL12 determination, and CXCR4 antibody determination
 - iv. Echocardiography
 - v. Lung function with 6-minute walk test
 - vi. Collection of indices for probability of progression (analogous to the INBUILD study, Flaherty et al. 2019), extent of lung involvement (according to Goh et al. 2008) and activity index according to EUSTAR (Valentini et al. 2017).
 - vii. ANA/ENA, fibrillarin, RNA polymerase III, myositis line blot
- e. Performance of a CXCR4 PET/CT scan
- f. Routine clinical check-ups are performed after 6 and 12 months, including points i.-vi.
- Follow-up checks of ILD using chest CT are performed after 12 months, in accordance with routine clinical practice.

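### Nothing in the protocol separates the PET uptake result from later treatment and follow-up ratings, so the uptake–progression association will be hard to interpret

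*Protocol*

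**What the plan says.** - **Hypothesis (section 4):** besides a correlation with disease activity, the study tests "that activity is associated with disease progression, i.e., worsening fibrosis in the corresponding organ".
- **Follow-up data (sections 5.1 and 6.3):** routine 6- and 12-month parameters enter the evaluation. Section 6.3 states: "Routine clinical check-ups are performed after 6 and 12 months, including points i.-vi". These points include mRSS, cardiac markers, echocardiography, lung function and the progression, extent and activity indices. A routine chest CT follows at 12 months.
- **Where the PET result goes (section 9):** "The evaluation of the collected image data is stored in SAP as a findings document". The data for the evaluation "is also stored as a pseudonymized Excel file, which contains only the data and the study code of the respective patient". No access rule is given for either copy.
- **Blinding (section 2, synopsis):** "Explorative, prospective pilotstudy, not blinded, not randomized".
- **Therapeutic relevance (section 3):** "Active inflammation can be treated much more effectively with medication than fibrosis".
- **Consent (section 10):** "There is no connection between the treatment of patients and participation in the study".
- **Primary endpoint (section 5.2):** "The primary endpoint of the pilot series is to determine the maximum measurable" tracer uptake in the fibrotic lung areas, at the one scan.

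**The concern.** A study of whether a test result predicts outcome needs the result not to influence that outcome or how it is measured. Two routes are open here.

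1. **Treatment.** The background section describes inflammation as the stage that responds to medication. A physician who learns of high uptake therefore has a reason to act on it. If the action works, patients with high uptake worsen less and a true association shrinks.
2. **Rating.** Someone who scores mRSS, the activity index, echocardiography or CT extent while knowing uptake may score in the expected direction. That creates or enlarges an association.

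Section 6.3 lists no data on treatment between scan and 12 months, so the first route could not be recognised afterwards from the planned data. This concerns access and data collection during the study, so a later analysis plan could not repair it. It matters beyond the pilot because section 4 says the data are to support the sample-size calculation for a subsequent study.

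**Working it through.** **1. The plan's own figure.** The appendix plans for a Pearson correlation of −0.75, two-sided α = 0.05 and power 0.80, and obtains 11 patients, 12 in total. The Fisher approximation gives ((1.960 + 0.842)/atanh 0.75)² + 3 = 11.29. Simulated power of the t-test for r is 0.780 at n = 10 and 0.825 at n = 11, so 11 is reproduced. This point disputes no figure. The −0.75 describes uptake against lung function in another disease, so using it below for progression is an assumption.

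**2. The chain in the text.** Patients are screened in the rheumatology outpatient clinic (6.3), and study data are kept there (9). Rheumatology supplies two of the four scientific directors (1.1). The PET evaluation is filed as a findings document (9). Follow-up ratings and CT come later (6.3) and are set against uptake (4). No step restricts knowledge of uptake, and points i–vii of 6.3 include no treatment variable.

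**3. Illustration, treatment route.** All inputs are assumed. Let U ~ N(0,1) be uptake and let untreated worsening have SD 1 and correlation ρ with U. Extra treatment lowers worsening by d SD in everyone above the median of U. Then

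- covariance = ρ − 0.399d
- variance = 1 + 0.25d² − 2(0.399)ρd
- observed r = covariance/√variance

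For ρ = 0.6 and d = 0.5: 0.4005/√0.8231 = 0.44. If a random half of those patients are treated, 0.399 becomes 0.1995 and 0.25 becomes 0.1875: 0.5003/√0.9272 = 0.52.

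| d (SD) | ρ = 0.6, all above median | ρ = 0.6, half of them | ρ = 0.75, all above median | Power at n = 11 (ρ = 0.75, Pearson) |
|---|---|---|---|---|
| 0 | 0.60 | 0.60 | 0.75 | 83% |
| 0.5 | 0.44 | 0.52 | 0.63 | 57% |
| 1.0 | 0.23 | 0.41 | 0.43 | 27% |
| 1.5 | 0.00 | 0.29 | 0.19 | 8% |

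If only the top quarter is treated (ρ = 0.75), d = 0.5 gives 0.66 with 64% power and d = 1.0 gives 0.51 with 38%.

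**4. Illustration, rating route.** With no true association and ratings shifted up by d in the high-uptake half, r = 0.399d/√(1 + 0.25d²). For d = 0.25, 0.5 and 1.0 this gives 0.10, 0.19 and 0.36.

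**5. Both together.** If both shifts fall on the same patients, only their difference enters the model. The sign of the net bias is therefore not determined, and the planned data give no means of separating the two.

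**6. What is not exposed.** The primary endpoint and the baseline correlations do not depend on anything after the scan. Laboratory values are little open to rating bias, though a treatment change could move them.

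**The case against.** - **The design is openly unblinded, exploratory and small.** True, and it is a legitimate choice for a pilot. Declaring it discloses the exposure but does not control it.
- **Access is not established.** A reader might infer from section 9 that treating physicians see the result and that the same physician later rates the outcome. The protocol gives no access rights and names no rater or CT reader, and radiology is a separate participating institute. That SAP means the hospital system is also a reading. The text supports only that nothing prevents such knowledge.
- **Section 10 might be read as contradicted by the filing.** It stands beside voluntariness and withdrawal and most naturally means that care does not depend on taking part. It is neither contradicted nor an access rule.
- **The filing sentence is not the root cause.** This stands. Moving the evaluation into a research file held by rheumatology would conceal nothing, and patients may ask for their stored data (section 9).
- **Chance swamps the bias.** At n = 12 and r = 0.6, the 95% Fisher interval is tanh(0.693 ± 1.96/3), or 0.04 to 0.87. It contains every ρ = 0.6 value in the table except 0.00. This is fair, but an interval shows sampling error and does not show this bias.

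**Conclusion.** The point holds as a weakness of one stated aim. The uptake–progression association rests on follow-up that nothing protects from knowledge of the scan, and post-scan treatment is not among the listed data. The possible distortion is material under moderate assumptions (0.60 to 0.44, or a spurious 0.19, for a shift of 0.5 SD). However, the documents give neither the frequency nor the effect of any treatment change, nor the size of any rating shift, so no estimate of the actual bias is possible and its direction is open.

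A reader might infer that the main result is compromised. It is not: the primary endpoint and baseline correlations are untouched, and section 5.2 does not name progression as an endpoint in its own right.

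**What to change.** Amend sections 6.3 and 9:

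1. Nuclear medicine holds the uptake evaluation (SUVs, ratios, visual grading) in its own pseudonymised file until each patient's 12-month data are complete.
2. Existing radiology readers score the 12-month CT extent without access to those values. The follow-up mRSS and activity index are likewise rated without them.
3. Treatment changes between scan and 12 months are recorded, together with whether the PET result was known.

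The sponsor should separately define how clinically relevant imaging findings are released, and state whether uptake results may inform care. Section 7.1 does not settle this, since it covers adverse events only. These are the sponsor's decisions. If results are to reach treating physicians, items 2 and 3 still make the association easier to interpret.

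The cost is minor access arrangements, a few extra eCRF fields and any matching wording in the patient information. Because rheumatology co-runs the study, masking of the clinical ratings may be incomplete; the CT scoring is the easiest part to protect.
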